##### 8.4.2. Exclusion criteria

- Requiring a high flow cannula, any ventilation or ECMO during first 24 hours post baselinec
- Pregnant
- Chronic kidney disease
- RDV initiated  $> 24$  hours post baselined
- Is a COVID-19 re-admission (was previously hospitalised for COVID-19)
- Missing Day 1 Daily Treatment CRF
- Missing ‘Medication’ section of the Outcome CRF

---

a RDV was recommended in people aged 12 and over, and weighing over 40kg. Weight was not generally measured at baseline for practical reasons, so we have excluded children aged 12-17 in order to be sure that no-one in the control group was likely to weigh less than 40kg.

b This criteria is an ideal, to measure the effectiveness of RDV initiated close to baseline. If RDV is more routinely given later than this, we will either remove this criteria, or move the window of inclusion to say 3 days. Statistics describing when RDV treatment was initiated compared with baseline, will be presented.

c This subgroup will be analysed separately (see Section 19).

d See footnote b above.

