### 8.2. Treatments studied

The key treatment of interest is RDV, given to patients at the early stage of a COVID-19 infection who have a high probability of developing severe disease. Guidelines were in place for its use in the UK – it was recommended for newly hospitalised patients, no later than within 10 days of symptom onset, and only initiated in non-ventilated patients. Patients were recommended to receive 200mg on Day 1 of treatment, followed by 100mg daily for 4 days. An optional additional 5 days of 100mg daily was recommended till 29th September, but the wording changed over time:

26th May to 2nd June: “If a patient does not demonstrate clinical improvement”

3rd June to 28th September: “If a patient deteriorates and progresses to ventilation and/or ECMO treatment”

29th September onwards: “Ensure that clinicians prescribe a maximum treatment course of 5 days” – this was due to a disruption in supply of the drug. It is stated that some exceptions may receive additional doses, but these were undefined by the guidelines.

The comparison treatment is: Standard of care, without RDV.

NB: Standard of care evolved as knowledge of the disease and how to treat it evolved. Co-medication with the corticosteroids dexamethasone and hydrocortisone became recommended for some patients part-way through our study period – these are not expected to interact with RDV, and so we expect that RDV patients will have received these in the same way as non-RDV patients. The drugs Hydroxychloroquine and Chloroquine phosphate were not recommended as concomitant medications for RDV from 3rd September 2020.

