### 8.3. Baseline: definition

We take a common baseline to be ‘date of hospitalisation due to COVID’. It is important to note that this is not necessarily when RDV was initiated, though it is likely that it was administered soon after admission. The definition of baseline depends on the where the infection was acquired:

Community acquired COVID-19 i.e. admitted with symptoms consistent with COVID-19:

Baseline = Date of admission to hospital

For hospital acquired COVID-19 :

Baseline = Date positive COVID-19 test was collected

‘Hospital acquired’ is defined as: symptom onset at least 5 days after hospital admission.

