##### 8.4.1. Inclusion criteria

- Laboratory confirmed SARS-CoV-2 infection
- Hospitalised
- Aged  $\geq 18$  yearsa at baseline
- Requiring supplementary oxygen ( $SpO_2 \leq 94\%$ ) at any time during 24 hours post baseline
- RDV initiated  $\leq 24$  hours post baseline (RDV group only)b

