## 17.2. Analysis of Outcomes

### 17.2.1. Primary Outcome

The percentage of patients that died by the end of day 14 will be presented for each group. Risk of death will be modelled using logistic regressionf,10, with treatment group fitted as a covariate, and ideally adjusting for the key confounders: age, sex, and number of comorbidities at baseline. The odds-ratio comparing RDV with controls, estimated from the model, will be presented together with a 95% CI and a p-value.

Note on adjustment for confounders: the number of covariates that may be added to the model depends on the number of deaths recorded (rule of thumb, 10 events per covariate fitted). Clinical trials data indicate that 14-day mortality for RDV in this type of patient may be around 3.1%, meaning that if we include 500 RDV-treated patients, we might expect 16 deaths from that group. Under the assumption that the risk of death is not lower in the control group, this suggests at least 32 deaths (under 1:1 matching), and so we project that there will be sufficient power to enable adjustment for 3 confounders given the higher expected matching ratio.

---

f Stuart (2010) recommends that in the analysis of cohorts matched using propensity scoring, it is more common to simply pool all the matches into matched treated and control groups and run analyses using the groups as a whole, rather than using the individual matched pairs.

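### Time zero is hospitalisation but RDV group membership is fixed by a later event, and the footnotes to 8.4 let that window widen or disappear without moving time zero

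*SAP*

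**What the plan says.** - **Time zero.** Section 8.3: "We take a common baseline to be ‘date of hospitalisation due to COVID", with the positive-test date used for hospital-acquired infection. The same section concedes that "this is not necessarily when RDV was initiated, though it is likely that it was administered soon after admission". Section 8.1 runs the time-scale from baseline to day 28.
- **RDV group.** Section 8.4.1 requires RDV to have started within 24 "hours post baseline (RDV group only").
- **Late starters.** Section 8.4.2 excludes anyone whose RDV began more than 24 h after baseline.
- **Fallback.** Footnote b to section 8.4 (footnote d refers back to it) says that if RDV is routinely given later, "we will either remove this criteria, or move the window of inclusion to say 3 days". It promises descriptive statistics on start times, but no change of time zero.
- **Early events.** Section 8.4.2 excludes, in both groups, patients "Requiring a high flow cannula, any ventilation or ECMO during first 24 hours post baseline". No equivalent rule covers death or discharge in that period.
- **Primary analysis.** Section 17.2.1: "The percentage of patients that died by the end of day 14 will be presented for each group", followed by a logistic regression with treatment group as a fixed covariate. The time-to-event outcomes use Cox models, also with fixed treatment group.

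**The concern.** Treatment status is set by something that happens after follow-up begins. Every RDV patient has, by construction, survived in hospital to the first dose. A patient who was going to receive RDV but died or went home first is counted as a control. Three features follow.

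1. The early period is handled as a landmark for ventilation but not for death or discharge.
2. Excluding late starters conditions on a future event: those who survive to a late dose leave the comparator, and those who die waiting for one stay in it.
3. The fallback applies exactly when starts are late, which is when the misalignment is largest, and the window is chosen after the data are seen.

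Propensity matching (8.7) uses baseline variables only. It does not require a control to be alive and in hospital when its matched patient started RDV. The balance check uses sex, age and comorbidity count, so it cannot show the problem. At stake is the primary odds ratio in a study that tests superiority on mortality, and the time-to-event outcomes as well.

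**Working it through.** **The plan's own figure.** Section 17.2.1 takes 3.1% mortality in 500 RDV patients: 500 × 0.031 = 15.5, stated as 16, and 2 × 16 = 32 deaths at 1:1. This reproduces. The SAP gives no figure for bias.

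**Inputs.** From the SAP: 14-day mortality R = 3.1%; 500 RDV patients; matching 1:1 to 1:4; window W of 24 h, about 3 days, or no limit. Assumed, because the SAP gives no values: a share q = 20% to 50% of eligible patients intended for RDV; intended start S uniform over the window; no drug effect. For the removed criterion I take starts over 0–10 days as a worst case. The only 10-day figure in the SAP, "no later than within 10 days of symptom onset" (8.2), is a guideline counted from symptom onset, not from baseline.

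**Deaths only, constant hazard.** λ = −ln(0.969)/14 = 0.00225 per day, and P(D<S) is the chance of dying before the intended start.

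- RDV risk = (R − P(D<S)) / (1 − P(D<S))
- Control risk = [(1−q)R + q·P(D<S)] / [(1−q) + q·P(D<S)]

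*24 h:* P(D<S) = 0.00112. RDV risk = 0.02988/0.99888 = 0.0299. Control risk = 0.0313 (q = 20%) or 0.0321 (q = 50%). Odds ratio 0.955 or 0.930.

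*3 days:* P(D<S) = 0.00337. RDV risk 0.0277; control risk 0.0318 or 0.0343. Odds ratio 0.868 or 0.804.

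*0–10 days:* RDV risk 0.0201; control risk 0.0337 or 0.0417. Odds ratio 0.587 or 0.470.

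**Adding discharge.** Take discharge at an assumed g = 0.1/day and choose λ so that (λ/(λ+g))(1 − e^(−14(λ+g))) = 0.031, giving λ = 0.0042. Let h(s) = e^(−(λ+g)s) be the probability of still being in hospital and undosed at s, and I(t) = (λ/(λ+g))(1 − e^(−(λ+g)t)) the cumulative incidence of death.

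- RDV risk = mean[h(S)·I(14−S)] / mean[h(S)]
- Control risk = [(1−q)R + q·mean I(S)] / [(1−q) + q(1 − mean h(S))]

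RDV against control risks are 0.0305 against 0.0311–0.0315 (24 h), 0.0295 against 0.0313–0.0322 (3 days) and 0.0253 against 0.0318–0.0336 (0–10 days).

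**Null odds ratio for 14-day death, q from 50% to 20%**

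| Start window | Deaths only, constant hazard | Deaths only, early-peaking (Weibull shape 0.7) | Deaths only, late-peaking (shape 1.5) | Constant hazard, discharge 0.1/day |
|---|---|---|---|---|
| 24 h | 0.93–0.96 | 0.83–0.89 | 0.98–0.99 | 0.97–0.98 |
| 3 days | 0.80–0.87 | 0.66–0.76 | 0.92–0.95 | 0.91–0.94 |
| 0–10 days (assumed worst case) | 0.47–0.59 | 0.36–0.48 | 0.61–0.71 | 0.75–0.79 |

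The deaths-only values hardly change at 10% or 20% mortality.

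**Net sign.** In a simulated mix of 75% fast-discharge and 25% severe patients, again with no drug effect, the odds ratio was 1.04 (24 h), 1.10 (3 days) and 1.13 (0–10 days), that is, against RDV.

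**Time-to-recovery.** Discharge is the event and undosed early discharges become controls. With discharge at 0.1/day and deaths kept at risk to day 28 as in 17.2.2.1, the null recovery rate ratio (RDV/control) was 0.91–0.94 (24 h) and 0.78–0.85 (3 days), against RDV.

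**Exclusion of late starters.** Keep the 24 h rule, q = 20%, deaths only, constant hazard, and let a further 10%, 20% or 40% be intended to start between day 1 and day 10. Those dying before that start stay as controls and the rest are removed. The odds ratio moves from 0.955 to 0.90, 0.84 or 0.68.

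**Random error.** SE(log OR) = √(1/(500 × 0.031 × 0.969) + 1/(m × 0.031 × 0.969)). For m = 500 controls this is 0.365, so the 95% limits multiply or divide the odds ratio by e^(1.96 × 0.365) = 2.04. For m = 2000 it is 0.288, factor 1.76. The constant-hazard, deaths-only bias at 24 h is 500 × (0.0313 to 0.0321 − 0.0299) = 0.7 to 1.1 deaths per 500 patients.

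**Landmark check.** Simulating with both groups alive, in hospital and counted from the end of the window returned a null odds ratio of 0.99 to 1.01 in every scenario.

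**The case against.** The rule as written is 24 h, and there the effect is about one death per 500 patients, well inside the sampling error. The wider window is conditional, and section 8.3 expects RDV soon after admission. Excluding patients without a Day 1 Daily Treatment CRF, in both groups, may remove some very early deaths and discharges. Section 11 admits that observational data limit what can be concluded. All of this is fair as to the size of the 24 h bias. None of it aligns time zero, and the Day 1 form does not make a control survive as long as its matched patient did before dosing.

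Two stronger readings are tempting. A reader might infer that the whole bias makes an inactive drug look protective, in the primary and all time-to-event outcomes. The SAP does not support that: guaranteed survival acts in that direction, but early discharge works against it and can reverse the net mortality result, and time-to-recovery is biased the other way. A reader might also take 0.47–0.59 as the expected odds ratio if the criterion is dropped. That needs starts spread evenly over ten days from admission, which nothing in the SAP supports and section 8.3 contradicts, and it ignores discharge.

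**Conclusion.** The plan is wrong as written: time zero, eligibility and treatment assignment are not aligned, and no landmark, time-dependent exposure or matching on time at risk corrects this. The bias in the primary odds ratio is small under the 24 h rule and becomes material at 3 days. If the criterion is removed it could be large, though only under the assumed worst case. These sizes rest on the assumed share intended for RDV, the start times, the hazard shape and the discharge pattern, none of which the SAP gives; the net sign for mortality cannot be stated in advance. Excluding late starters adds a bias in RDV's favour through deaths, of a size that depends on how many start late. The main fault is the open-ended footnote, and it should be settled before analysis.

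**What to change.** 1. Set a landmark at the end of the RDV start window: 24 h by default, and moved with the window for both groups if it is widened. Include only patients alive, in hospital and not ventilated at the landmark, classify RDV by starts up to it, and begin follow-up there.
2. Count 14-day mortality from the landmark. That ends at day 15 post baseline for 24 h and day 17 for 3 days, both inside planned follow-up. End the 28-day outcomes at day 28 post baseline, because follow-up stops there (8.8).
3. Alternatively, match each RDV start on day d to a control alive, in hospital, unventilated and untreated on day d, with both clocks starting on day d.
4. Do not remove patients from the comparator because they start RDV after the landmark. Keep them as non-RDV in the main analysis. Censor them at RDV start only in a time-to-death sensitivity analysis, noting that this censoring may be informative; it cannot be done in the binary logistic primary analysis.
5. Replace footnotes b and d, deleting the option to drop the criterion with time zero left at admission.

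**Cost.** SAP wording and programming, with no new data collection. Deaths and discharges before the landmark leave the comparison, the 28-day outcomes lose the landmark interval, and keeping late starters as controls slightly dilutes the contrast.

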### 8.5. Consent process

All endpoints defined in this study are derived from data that can be obtained from hospital records. As part of the ISARIC WHO clinical characterisation protocol, multiple time point biological sampling is also recorded prospectively – for this, consent from patients must be obtained. Use of biological data however, are beyond the scope of the objectives of this analysis plan.

### 8.6. Blinding

Neither clinicians nor patients are blinded to treatments allocated.

### 8.7. Definition of treatment groups

The analysis cohort will be split into two treatment groups: RDV and non-RDV. As the study is observational, allocation of treatment is decided by clinicians.

A matching process will be carried out to link RDV patients with non-RDV patients as follows:

A logistic regression with dependent variable RDV (Yes/No) will be fitted including the following covariates:

1. Month of baseline
2. Tier of participating centre (0 / 1 and 2)
3. Sex
4. Age
5. Broad ethnicity group (White / Asian / Black / Other)
6. Clinically extremely vulnerable status (Yes: Cancer / Yes: Severe respiratory condition / Yes: on immunosuppression therapy / Yes: Other / No)
7. Comorbidities: Diabetes (Y/N), Hypertension (Y/N), Obesity (Y/N), Chronic Cardiac disease (Y/N), CPD (Y/N), Asthma (Y/N)
8. Where COVID was acquired (Community / Hospital)
9. Admitted to HDU/ICU at baseline (Y/N)

Note: a pragmatic approach will be taken – the list above defines a best-case set of matching criteria; it may be necessary for categories to be collapsed to simplified discriminators (e.g. White vs Other ethnicity, or ‘Total number of comorbidities’), should the model become over-parametrised. If possible, 2nd order interactions will be investigated, and if statistically significant, added to the model. All main effects will be retained in the model, even if not significant.

The fitted model will be used to calculate the probability of receiving RDV for each patient according to their baseline factors. The probability calculated is called their propensity score (PS). Boxplots will

be presented showing the distribution of PS in each treatment group. Patients who were given RDV will then be matched to a control patient / patients with a similar PS who did not get RDV, using a nearest neighbour matching algorithm and a pre-specified maximum difference in PS (calliper width) of 0.2 standard deviations. The ratio of RDV patients to controls may be 1:1 or higher – to a maximum of 1:4 (Rassen (2012) suggests that 1:n matching leads to higher precision in estimating effect sizes, with a cost of a small increase in bias with increasing n). Controls are chosen without replacement, so may not be matched to more than one RDV patient.

The matched cohort will be checked for balance, by using the disease risk score diagnostic described by Stuart (2013): an underlying primary outcome risk score will be calculated using the following analysis dataset: all non-RDV patients satisfying inclusion/exclusion. The primary outcome will be modelled using logistic regression, and the following key risk factors will be fitted as covariates: sex, age, and number of comorbidities. (These are chosen from Knight 2020^9, and as being the most measurable for most members of the cohort.) The fitted model will be used to calculate a primary outcome risk score (RS) for each patient included in the matched cohort. The mean and SD of RS will be calculated for each treatment group. The groups will be checked for balance by calculating the absolute standardised difference in RS:

$$ASD_{RS} = \frac{|\overline{RS}_T - \overline{RS}_C|}{\sqrt{\frac{s_T^2}{2} + \frac{s_C^2}{2}}}$$

Where  $s_T$  and  $s_C$  are the standard deviation of RS in RDV and control groups respectively.

If  $ASD_{RS} < 0.1$ , the matching will be considered balanced.

If matching is found to have been unsuccessful in balancing treatment and control groups, the propensity score model will be revised.

Patients from either treatment group that are not matched will be excluded from inferential analyses, and will be described separately.

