## 8. Study design

### 8.1. Overall study design

This is a prospective, observational non-interventional matched cohort study, within the ISARIC 4C CCP, of hospitalised patients with severe COVID-19. Patients treated with RDV will be compared with matched controls (or if this is infeasible, with all patients satisfying key inclusion/exclusion criteria – see below). The time-scale is from baseline to 28 days post baseline.

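### Balance is judged on a score of sex, age and comorbidity count alone, so a cohort imbalanced on other propensity covariates can pass and the primary odds ratio may be biased

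*SAP*

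**What the plan says.** SAP Section 8.7 models receipt of remdesivir (RDV) on nine groups of covariates. The list starts with "Month of baseline" and includes centre tier, sex, age, ethnicity, vulnerability status, individual comorbidities, place of acquisition and HDU/ICU admission. RDV patients are matched within a calliper of 0.2 SD at ratios from 1:1 to 1:4, and "Controls are chosen without replacement, so may not be matched to more than one RDV patient". Neither Section 8.7 nor Section 10 says whether the ratio is a single study-wide figure or differs between matched sets.

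Balance is then checked with a risk score for the primary outcome, fitted in non-RDV patients: "the following key risk factors will be fitted as covariates: sex, age, and number of comorbidities". If the ASD of that score (ASD_RS) is below 0.1, "the matching will be considered balanced". The consequence of failure is stated too: "If matching is found to have been unsuccessful in balancing treatment and control groups, the propensity score model will be revised". No other numerical criterion appears.

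The primary logistic model (Section 17.2.1) adjusts, ideally, for the same three factors. Its footnote f cites advice to "simply pool all the matches into matched treated and control groups". Weights are not mentioned. Section 17.1 tabulates baseline characteristics of the matched cohort by group. Sections 8.7 and 18 allow PS covariates to be collapsed or dropped. Section 8.1 allows a comparison without matching: "or if this is infeasible, with all patients satisfying key inclusion/exclusion criteria".

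**The concern.** The acceptance rule tests what the outcome regression would handle anyway and leaves untested what the regression omits. Month, centre tier, ethnicity, vulnerability status, place of acquisition and HDU/ICU admission are in the PS because they may drive treatment choice. After matching they are neither gated nor adjusted for. If matching fails on one of them, the rule can still report success, the PS model is not revised, and the residual confounding goes into the primary OR. Month matters particularly, because Section 8.2 says that standard of care evolved during the study and Section 6 dates UK availability of RDV from 26 May 2020.

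**Working it through.** **1. The plan's own event figures.** Section 17.2.1 takes 500 RDV patients and 3.1% mortality: 500 × 0.031 = 15.5, rounded up to 16, and 2 × 16 = 32 deaths under 1:1 matching. Both figures reproduce. With 10 events per covariate, 32 deaths support about three covariates. At 1:4, 2,500 × 0.031 = 77.5 deaths support about seven. Regression therefore cannot take in every PS covariate, and the matching has to balance the rest.

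**2. What the check can see.** The risk score is a function of sex, age and comorbidity count only. Its group means and SDs, and so ASD_RS, depend only on how those three are distributed in each group. A covariate unrelated to them leaves ASD_RS unchanged however imbalanced it is.

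**3. Size for one binary factor (closed form, no treatment effect).** Assumptions: control risk 3.1% (the SAP's RDV rate), and a factor such as HDU/ICU that is unrelated to the three score variables.

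Example: prevalence 10% in RDV and 20% in controls, factor–death OR 3.
- ASD = 0.10 / √((0.09 + 0.16)/2) = 0.28.
- Risk without the factor, p0, solves 0.8·p0 + 0.2·3p0/(1 + 2p0) = 0.031, so p0 = 0.0226; risk with the factor is 0.0648.
- RDV risk = 0.9 × 0.0226 + 0.1 × 0.0648 = 0.0268.
- Spurious OR = (0.0268/0.9732)/(0.031/0.969) = 0.86.

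| Prevalence RDV / control | ASD | OR if factor–death OR is 2 | 3 | 4 |
|---|---|---|---|---|
| 10% / 15% | 0.15 | 0.96 | 0.93 | 0.90 |
| 10% / 20% | 0.28 | 0.92 | 0.86 | 0.82 |

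**4. Whether such cohorts pass (simulation, true OR 1).** Greedy nearest-neighbour matching without replacement, up to 1:4, calliper 0.2 SD of the logit PS, primary model adjusted for age, sex and comorbidity count. Assumed log odds of treatment: +0.35 per month, +1.0 for HDU/ICU, −1.0 for hospital acquisition. Assumed log odds of death: −0.25, +1.2 and +1.0 respectively. ASDs are averages over cohorts; the last two columns give the OR without and with control weights of 1/set size.

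| Scenario (cohorts) | Controls per RDV patient | ASD_RS | Share passing | ASD month / HDU-ICU / acquisition | OR unweighted | OR weighted |
|---|---|---|---|---|---|---|
| Full PS, ample controls (60) | 3.92 | 0.022 | 100% | 0.02 / 0.04 / 0.02 | 1.002 | 0.999 |
| PS cut to the three score factors (60) | 4.00 | 0.013 | 100% | 0.59 / 0.37 / 0.29 | 0.855 | 0.855 |
| Full PS, scarce controls, variable ratio (200) | 3.12 | 0.089 | 65% | 0.18 / 0.17 / 0.06 | 1.058 | 1.054 |
| Full PS, scarcer controls, variable ratio (200) | 2.43 | 0.113 | 33% | 0.31 / 0.17 / 0.11 | 0.926 | 0.963 |

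Monte Carlo standard errors on the log OR are 0.02 to 0.03. In the two variable-ratio scenarios, every cohort that passed had an ASD above 0.1 for month, HDU/ICU or acquisition.

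The two scarce-control settings were rerun with a fixed 1:4 ratio, which left 251 and 167 RDV patients. Of these cohorts 94% and 83% passed, and 12% and 31% of the passing ones had such an ASD. Weighting changes nothing there (OR 1.013 and 0.927 either way). The 0.927 comes with average covariate ASDs of only 0.04 to 0.06 in small cohorts, so I do not attribute it to imbalance.

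**The case against.** Four points deserve weight.

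- **The PS model already contains these covariates.** Section 8.7 keeps all main effects and shows PS boxplots by group, and with the full model and ample controls the simulated OR is 1.00. This stands, and it rules out the reading that the primary OR is biased as planned. It does not cover scarce controls at high PS, or the collapsing and dropping of covariates that Sections 8.7 and 18 allow.
- **The Section 17.1 table would show most imbalances.** It covers ethnicity, vulnerability status, comorbidities, place of acquisition and HDU/ICU. But it carries no threshold or action, and it omits month and centre tier. Section 15 considers adjustment for treatments received, not for baseline covariates.
- **Unequal sets pooled without weights are an inference.** A reader might conclude that the plan undoes its own match this way. Sections 8.7 and 10 can equally mean one fixed ratio, and footnote f contrasts pooling with analysing individual pairs without mentioning weights. In the table above weighting moved the OR by 0% to 4%. A separate set of 40-replicate simulations with other assumed effects gave larger gaps (1.06 against 0.97, and 1.14 against 0.99), so the size depends on the inputs. A gap of 1.24 against 1.01 can be produced with one strong confounder and no adjustment, but that is not the planned model.
- **The fallback in Section 8.1 is a parenthesis without a model.** A reader might infer that it drops month and centre from the adjustment. The SAP does not say so. It also does not say what adjustment would apply.

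It would also go too far to say that the other covariates cannot move the score. They can, through correlation with its three inputs.

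**Conclusion.** The point holds as a weakness in a stated rule: ASD_RS below 0.1 can declare balance while PS covariates outside the score are imbalanced, and the primary model does not adjust for them. Whether bias follows is conditional. Little is expected with the full PS and ample controls. Under the assumptions above, the simulated OR was 0.86 with a PS cut to three factors, and 1.06 and 0.93 with scarce controls and variable ratios, against a true 1.00. These fall on both sides of 1, so neither direction nor size can be predicted from the SAP. Prevalences and covariate effects are assumed throughout. The change should be made because it is cheap and because the present rule cannot tell the good case from the bad one.

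**What to change.** - Keep the ASD_RS check. Also require ASD below 0.1 in the matched cohort for the PS and for every covariate listed in Section 8.7, including month and centre tier, and including any covariate dropped from the PS model. If any fails, revise the PS model, or adjust for that covariate in the outcome model where events allow.
- State whether the matching ratio is fixed. If it varies between sets, weight each control by 1/(number of controls in its set) in the ASDs and outcome models, with robust standard errors. With a fixed ratio no weights are needed.
- If the unmatched fallback is used, adjust or weight by the same PS, including month of baseline.

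I would not enlarge the risk score to all PS covariates. Assuming seven months, that is 6 + 1 + 1 + 1 + 3 + 4 + 6 + 1 + 1 = 24 parameters (month, tier, sex, age, ethnicity, vulnerability, comorbidities, acquisition, HDU/ICU). By the SAP's rule this needs 240 deaths, about 240/0.031 ≈ 7,700 controls if their mortality is 3.1%, and fewer if it is higher.

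The cost is SAP wording, possibly another round of PS revision and, with weights, slightly wider intervals. Some failures will be chance: with 500 per group the standard error of an ASD is roughly √(1/500 + 1/500) = 0.063. This is why adjustment is offered as an alternative to repeated revision.
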